8.3.4. Tumor Response Rate

- Determination of tumor response will be performed on each subject in the PP population.
- The Tumor response rate of Ad-RTS-hIL-12 + velevidemex when administered in combination with cemiplimab will be estimated at 6, 12, 18 and 24 months.
- Tumor response will be defined by radiographic and clinical criteria. Complete response (CR) or partial response (PR) will be first assessed by radiographic changes that indicate a reduction of bi-dimensional tumor size as per Recist 1.1 criteria. In addition, changes in neurologic function and steroid use will be considered to determine stable disease (SD).

8.3.5. Best Overall Response (BOR)

The BOR was not originally included in the protocol and has been added as a new secondary endpoint. The BOR will be determined for each subject based on the applicable tumor assessment results for both the investigator and the IRC.

[figure not shown]
The best overall response (BOR) is a derived variable that summarizes for each treated subject the best tumor response recorded on the eCRF based on the investigator assessment.

- Tumor response data collected before evidence that the subject received a new anticancer treatment.

The BOR categories are defined as:

- Complete Response
- Partial Response
- Stable Disease
- Progressive Disease

- Not Evaluable (if subject has BOR assessment but is denoted Not Evaluable)
- No Response (if subject has no BOR assessment).

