The lack of standard and validated salvage therapies has prompted the use of nitrosoureas, temozolomide rechallenge, bevacizumab, and other targeted agents that are unsatisfactory treatment options. This likely reflects the complexities of disease heterogeneity, and the treatment limitations of brain tumors given the low activity of antineoplastic agents, de novo or acquired drug resistance, the sensitivity of the brain to irreversible damage in response to treatment and the presence of the blood brain barrier (BBB), which maintains the brain as a privileged compartment. Surgical resection may be offered for subjects with recurrent disease, with the goal of alleviating mass effect, improving symptoms, and achieving cytoreduction. Surgical resection, however, is limited by the infiltrative nature of the disease and the lack of clear margins delimitating the tumor. Given the poor overall prognosis and lack of effective treatments, new therapeutic approaches for malignant gliomas are needed.

Immunotherapy for brain tumors is actively being investigated with an array of newer therapeutic modalities. Only about a third of glioblastomas have been reported to demonstrate a robust CD8+ cell population present within the tumor microenvironment (Heimberger et al. 2008), and these cells are anergic (i.e., not secreting interferon gamma [IFN- γ] or incapable of cytolytic activity). The immune infiltration in glioblastomas is highly variable and is likely

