9.2. Exclusion Criteria

1. Radiotherapy treatment within 4 weeks of starting veledimex
2. Prior treatment with bevacizumab
3. Subjects receiving systemic corticosteroids for treatment of disease-related symptoms during the 4 weeks prior to Day -7
4. Subjects with clinically significant increased intracranial pressure (e.g., impending herniation or requirement for immediate palliative treatment) or uncontrolled seizures
5. Uncontrolled infection with human immunodeficiency virus, hepatitis B or hepatitis C infection; or diagnosis of immunodeficiency.

NOTE:

- Subjects with known HIV infection who have controlled infection (undetectable viral load (HIV RNA PCR) and CD4 count above 350 either spontaneously or on a stable antiviral regimen) are permitted. For subjects with controlled HIV infection, monitoring will be performed per local standards.
- Subjects with hepatitis B (HBsAg+) who have controlled infection (serum hepatitis B virus DNA PCR that is below the limit of detection AND receiving anti-viral therapy for hepatitis B) are permitted. Subjects with controlled infections must undergo periodic monitoring of HBV DNA. Subjects must remain on anti-viral therapy for at least 6 months beyond the last dose of investigational study drug.

- Subjects who are hepatitis C virus antibody positive (HCV Ab+) who have controlled infection (undetectable HCV RNA by PCR either spontaneously or in response to a successful prior course of anti-HCV therapy) are permitted.

6. Use of systemic antibacterial, antifungal, or antiviral medications for the treatment of acute clinically significant infection within 2 weeks of first veledimex dose. Concomitant therapy for chronic infections is not allowed. Subjects must be afebrile prior to Ad-RTS-hIL-12 injection; only prophylactic antibiotic use is allowed perioperatively.
7. Use of enzyme-inducing antiepileptic drugs (EIAED) within 7 days prior to the first dose of study drug. Note: Levetiracetam (Keppra®) is not an EIAED and is allowed.
8. Other concurrent clinically active malignant disease, requiring treatment, except for non-melanoma cancers of the skin or carcinoma in situ of the cervix or non-metastatic prostate cancer
9. Nursing or pregnant females
10. Prior exposure to veledimex
11. Use of an investigational product within prior 30 days.

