5. Seizures, headache, and cerebral edema are commonly observed in this population and will be recorded according to the grade of toxicity and therefore will not be considered in this category unless unresponsive to maximal medical support as directed by the Investigator (informed by institutional guidelines) and in consultation with the Sponsor Clinical Medical Monitor.
6. *Cerebral Edema Guideline Recommendations:* As a general guideline, mannitol (Osmotrol), corticosteroid treatment (i.e., dexamethasone or Decadron) and/or withholding the next dose(s) of veledimex short-term are considered for cerebral edema, CTCAE v5.0 Grade 3 (or for “moderate” severity descriptively). For Grade 4 cerebral edema, mannitol (Osmotrol), higher dose corticosteroids and/or longer-term withholding or discontinuation of veledimex are considered, especially if the edema is not sufficiently mitigated by urgent medical intervention. It is expected that the use of corticosteroids will vary between sites and among subjects, and therefore, the precise extent and dosage of steroids cannot be specified per protocol. The treating physician will decide as is safe and appropriate for the individual subject according to their clinical judgement as informed by the label and institutional guidelines and should consider the minimum steroid dose or the lowest amount that adequately and

rapidly controls the subject's signs and symptoms (refer to Rationale section below). Consideration also may be given to a limited number of doses of bevacizumab (Avastin) if (typically high-dose) corticosteroids are not in the best interests of the subject in the treating physician's clinical judgement and following consultation with the Medical Monitor. In the event of an immediately life-threatening event, the treating physician should consider surgical decompression.

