11. CONCOMITANT THERAPY

Information on concomitant medications, including all medications, blood products, vitamins, and other supplements, will be collected through the Screening, Treatment, through 90 days after the subject's last dose of any study drug.

Subjects experiencing brain tumor-related symptoms or edema should be treated with corticosteroids as per standard practice. The treating physician should consider the minimum starting steroid dose for study subjects, if determined that it is safe and appropriate for that individual patient. For study subjects who require a higher starting steroid dose, efforts should be made to taper steroids to the lowest amount that controls the subjects' symptoms, as determined to be safe and appropriate by the treating physician

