11.2. Prohibited Medications/Therapies

The following medications are prohibited during the study:

- Any other investigational agent or anticancer therapy (chemotherapy, radiotherapy, etc.) while receiving study treatment
- Palliative radiotherapy is not permitted while on study
- Enzyme inducing anti-epileptic drugs (EIAED) are listed in [Appendix 3](#) and are NOT permitted.
- Use of heparin or other anti-coagulation therapy, or acetylsalicylic acid (ASA), or anti-platelet drug within Day -7 to Day 21 should not be used unless necessary to treat a life-threatening illness

NOTE: Care should be given when prescribing medications to avoid the use of drugs that are classified as CYP450 3A4 inducers, inhibitors, or substrates due to interactions with the study drug, unless needed for urgent intervention. All medications should be recorded in the case report form as indicated in the completion guidelines.

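### SAP 8.3 does not settle how on-study bevacizumab or corticosteroids for oedema affect response and PFS, so shrinkage after rescue may be credited to the study regimen

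*SAP*

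**What the plan says.** **Rescue treatment.** Protocol Section 11 states: "Subjects experiencing brain tumor-related symptoms or edema should be treated with corticosteroids as per standard practice". Protocol 10.10, Table 2 note 6, adds: "Consideration also may be given to a limited number of doses of bevacizumab (Avastin) if (typically high-dose) corticosteroids are not in the best interests". The Medical Monitor has to be consulted first. The number of doses is not defined.

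**How the protocol treats bevacizumab elsewhere.** Section 6.1 says the lack of validated salvage therapy "has prompted the use of nitrosoureas, temozolomide rechallenge, bevacizumab, and other targeted agents". Section 9.2 lists "Prior treatment with bevacizumab" as an exclusion. Section 11.2 prohibits "Any other investigational agent or anticancer therapy (chemotherapy, radiotherapy, etc.) while receiving study treatment".

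**Scoring rules in the SAP.**
- ORR (8.3.3) uses confirmed response by RECIST 1.1 and expressly sets iRANO aside.
- Tumor response rate (8.3.4) takes CR and PR from radiographic change by RECIST 1.1, then says "changes in neurologic function and steroid use will be considered to determine stable disease (SD". Protocol 13.1 limits steroid use to stable disease in the same way, under iRANO.
- PFS (8.3.2) counts iRANO-confirmed progression or death. It censors for study discontinuation, loss to follow-up and the two-year limit.
- BOR (8.3.5) restricts the usable data: "Tumor response data collected before evidence that the subject received a new anticancer treatment".

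**Status of these endpoints.** SAP 10.2 lists PFS, ORR, tumor response rate and BOR among the analyses left out of the final analysis. The table lists in SAP Section 13 still carry BOR, ORR, ORR confidence interval and PFS tables.

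**The concern.** Response is meant to measure what the study regimen does to the tumour. Subjects with oedema may also receive a drug that the protocol itself names as a treatment for this disease, or corticosteroids, which Protocol 13.2 lists among the factors influencing contrast enhancement. If a later scan shows less enhancement, the written rules for ORR and tumor response rate give no reason to withhold CR or PR. The PFS rules give no way to see how far rescue delayed the recorded event.

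The trial has no control arm, and SAP 8.3 bases tumour endpoints on the investigator's reading. SAP 4.4 records that the imaging work planned with the external vendor was put on hold and not performed. A comparator or a completed central read would have offered some check on misattributed responses. As matters stand, the scoring rule has to provide it.

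**Working it through.** The plan states no figure for rescue use or its effect, so there is nothing to reproduce. The check compares the rules and then sizes the consequence.

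**1. Rules side by side**

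| Endpoint | Criteria | Cut-off or censoring for other active treatment | Steroid condition on CR/PR |
|---|---|---|---|
| ORR (8.3.3) | RECIST 1.1, confirmed | none stated | none stated |
| Tumor response rate (8.3.4) | RECIST 1.1 | none stated | none; stable disease only |
| BOR (8.3.5) | eCRF response | at new anticancer treatment, term undefined | none stated |
| PFS (8.3.2) | iRANO, confirmed | none stated | not applicable |

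The only cut-off belongs to BOR, and it is not repeated for the other three endpoints. Whether oedema bevacizumab triggers it is open. Protocol 6.1 and 11.2 could support treating the drug as anticancer therapy, while note 6 of Table 2 permits it as oedema care. Two programmers could reasonably code the same subject differently.

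**2. Size for ORR**

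Inputs: about 25 evaluable subjects planned (Protocol 16.2); 40 treated subjects in the full analysis set (SAP 4.4). The SAP does not give the per-protocol count.

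- Shift per misattributed response = 1/n: 1/25 = 4.0 points; 1/40 = 2.5 points.
- The number affected is not stated. Assuming 1 to 3 at n = 25: 1/25 = 4% to 3/25 = 12%.
- Exact (Clopper-Pearson) 95% intervals at n = 25: 0/25 gives 0 to 13.7%; 1/25 gives 0.1 to 20.4%; 3/25 gives 2.5 to 31.2%.

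For a wider range, assume a true ORR of 5%, a share q of subjects rescued, and a chance f that a rescued non-responder is scored CR or PR. None of these comes from the documents.

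- Inflation = q × f × (1 − 0.05).
- Low: 0.04 × 0.25 × 0.95 = 0.0095, about 1 point. Probability of at least one such case in 25 = 1 − (1 − 0.0095)^25 = 0.21.
- High: 0.30 × 0.50 × 0.95 = 0.1425, about 14 points. Probability = 1 − (1 − 0.1425)^25 = 0.98.

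**3. Size for PFS**

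MRI is every 8 weeks after Day 57. If rescue hides progression at one scheduled scan, the recorded event moves by at least 56 days. With the SAP 11.5 month of 30.4375 days, 56/30.4375 = 1.84 months. Protocol 6.1 cites a median PFS of 2 to 3 months.

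**The case against.** The strongest reply is that these endpoints have been withdrawn. SAP 10.2 removes them, the remaining primary endpoint is OS, and SAP Section 8 plans no formal testing. In one table list the PFS table is marked as not needed for now; in the other, the BOR, ORR and PFS rows name no source dataset, whereas the OS row does. This lowers the importance of the point. It does not dispose of it, because the tables remain listed and the protocol keeps the endpoints.

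A reader might also infer more than the documents support:

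- *That the plan has no rule at all.* It has one for BOR, which would exclude scans after bevacizumab if that drug counts as new anticancer treatment. The fault there is an undefined term. Nothing says oedema bevacizumab falls outside it.
- *That iRANO ignores steroids or bevacizumab.* Its text is not reproduced in Appendix 4, so this cannot be asserted. For PFS the supportable point is the missing sensitivity analysis. RECIST 1.1 is not reproduced either; the SAP simply adds no condition to it.
- *That the bias always favours the regimen.* Protocol 13.2 mentions corticosteroids when explaining increases in enhancement, and a steroid taper could work the other way. The baseline MRI falls within 24 hours (plus 48) of the injection. If steroid doses peak around surgery, later scans would mostly be taken on lower doses.
- *That several responders are affected.* Bevacizumab use is conditional and limited, and ORR requires confirmation, which a transient effect may not meet. The figure of 1 to 3 is an assumption.

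The Section 9.2 exclusion carries no weight here, since its synopsis counterpart is partly redacted.

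**Conclusion.** The gap is real but narrower than an absence of any rule. As written, ORR and tumor response rate can credit CR or PR after bevacizumab or on an increased steroid dose. BOR is ambiguous for bevacizumab and silent on steroids for CR and PR. PFS has neither a rule nor a sensitivity analysis for rescue or new therapy.

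The size is 4 points of ORR per case at n = 25, or 2.5 points at n = 40, with the number of cases unknown. The argument assumes that rescue can reduce measured enhancement enough to be scored as response. The documents make this plausible but do not quantify it. Severity is low to moderate: OS is untouched, and the point matters only if the response or PFS outputs are produced, on which SAP 10.2 and the table lists disagree.

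**What to change.** First reconcile SAP 10.2 with the table lists in Section 13. Then, for any of these tables or listings that are produced:

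1. State that any on-study bevacizumab, whatever its recorded indication, counts as new anticancer treatment for response scoring. Apply the BOR cut-off to ORR and tumor response rate as well.
2. Do not credit CR or PR on a scan taken while the corticosteroid dose is above that at the baseline MRI. If doses are highest around surgery, this condition will seldom apply.
3. Add a PFS sensitivity analysis, not a replacement, censoring at the last MRI before the first bevacizumab dose or new anticancer therapy.
4. Report how many subjects each rule affects.

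The sources are already planned: concomitant medications, Listing 16.2.4.7 (corticosteroid dosage) and Listing 16.2.4.8 (post-treatment anti-cancer therapy). The work is SAP wording plus a merge of medication dates with scan dates. The cost is that a few scans become unusable for response, ORR may be slightly lower, and the censoring in item 3 may be informative, which is why it should remain a sensitivity analysis.

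Protocol 10.10 note 6 and Section 11.2 must be reconciled by the sponsor. These are scoring rules only; no change to oedema care is proposed.

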8.4. Other Efficacy Endpoints: Karnofsky Performance Status (KPS)

The KPS measures the ability of cancer subjects to perform ordinary tasks. Scores range from 0 to 100 with a higher score meaning that the patient is better able to carry out daily activities. The KPS is used to determine a patient's prognosis and to measure changes in a patient's ability to function. Subjects must have a KPS score of ≥ 70 at the Screening Visit to be eligible to participate in the study.

KPS measures were planned to be taken at screening, Day -7, Day 0, Day 14, Day 36 and every 3 weeks thereafter. KPS observed values will be provided in listings. Originally planned, changes from baseline at each scheduled visit were to be performed to summarize descriptive statistics. See other efficacy variables under Section 10 describing the changes to the planned analysis.

9. SAFETY ANALYSIS

All analyses of safety will be conducted using the FAS. Abnormal laboratory test results, will be captured as Adverse Events (AE)s. Safety evaluations will use calculations to determine estimates of the incidence, intensity, and the type of AE and SAE's based on preferred term coding.

All clinical findings will be further inspected through a clinical review of relevant parameters including AEs, serious adverse events (SAEs), laboratory values (hematology, serum chemistry, and urinalysis), body weight, vital signs, physical examinations, and ECOG performance status. Where applicable the Safety will also be summarized using the ESP. Exposure to study drug and reasons for discontinuation of study treatment will be tabulated.

9.1. Adverse Events

9.1.1. Treatment-Emergent Adverse Effects (TEAE)s

The primary presentation of AE's will be prepared without regard to causality or relationship to study treatment. In addition, summaries of all TEAEs, treatment-related TEAEs and of all SAEs will be tabulated by System Organ Class (SOC), Preferred Term (PT), and Common Terminology Criteria for Adverse Events (CTCAE) grade of TEAE.

A TEAE is defined as an AE that meets any of the following conditions:

- Begins on or after the first dose of study drug and before the stop of study drug + 90 days.
- Begins before the first dose of study drug and worsens in severity on or after the first dose of study drug and before the stop of study drug + 90 days.
- Is completely missing an onset date and an end date.
- Is completely missing an onset date and the end date is on or after the first dose of study drug.

Verbatim terms captured on the eCRF will be mapped to PTs and SOC using the Medical Dictionary for Regulatory Activities (MedDRA®) Version 23.0 or higher for purposes of TEAE summarization.

9.1.2. Incomplete Onset or end date Imputation Conventions

If the onset date or the end date of an AE is incomplete, the following conventions for date imputation of the AE onset and end dates will be applied.

Missing onset dates (where UK and UKN indicate unknown or missing day and month respectively):

- UK-MMM-YYYY: If the month and year are different from the month and year of the first dose of study drug, assume 01-MMM-YYYY. If the month and year are the same as the first dose of study drug month and year, and the end date (after any imputation) is on or after the first dose of study drug, then assume the date of the first dose of study drug. If the month and year are the same as the first dose of study drug

month, and year and the end date (after any imputation) is prior to the first dose of study drug, then assume the end date for the onset date.

- DD-UKN-YYYY/UK-UKN-YYYY: If the year is different from the year of first dose of study drug, assume 01-JAN-YYYY of the collected year. If the year is the same as the first dose of study drug year, and the end date (after any imputation) is on or after the first dose of study drug, then assume the date of the first dose of study drug. If the year is the same as the first dose of study drug, and the end date (after any imputation) is prior to the first dose of study drug, then assume the end date for the onset date.

Missing end dates (where UK and UKN indicate unknown or missing day and month respectively):

- UK-MMM-YYYY: Assume the last day of the month.
- DD-UKN-YYYY/UK-UKN-YYYY: Assume 31-DEC-YYYY.

9.1.3. Incidence of Adverse Events

An overview summary of the number and percentage of subjects with any TEAE, serious TEAE, study drug-related TEAE, study drug-related serious TEAE, TEAE leading to treatment discontinuation, TEAE leading to study termination, and AE leading to death will be presented.

Summaries of the total number of TEAEs and the number and percentage of subjects with at least one TEAE will be provided. The number and percentage of subjects and the number of events will also be presented by SOC and PT. At each level of summarization, a subject is counted once if the subject reported one or more events. Percentages will be calculated out of the number of subjects in the FAS. The number of events at each level of SOC and PT will also be summarized.

A summary of TEAEs will also be presented in descending order from the SOC with the highest total incidence to the SOC with the lowest total incidence. If the total incidence for any two or more SOCs is equal, the SOCs will be presented in alphabetical order. Within each SOC, the PTs will be presented in alphabetical order.

All AEs will be provided in subject listings.

9.1.4. Relationship of Adverse Events to Study Drug

A summary of TEAEs by relationship (i.e., “Related” and “Not Related”) to Ad-RTS-hIL-12 + veledimex and cemiplimab will be presented separately in a table by incidence of occurrence. The investigator will provide an assessment of the relationship of the event to the study drug. The possible relationships are “Not Related”, “Unlikely”, “Possible”, “Probable”, and “Definite”. In the TEAE relationship table, if a subject reports multiple occurrences of the same TEAE, only the most closely related occurrence will be presented. TEAEs that are missing a relationship or with a relationship other than “Not Related” or “Unlikely” will be presented in the summary table as “Related” but will be presented in the data listing with a missing relationship or the actual relationship respectively. Percentages will be calculated out of the number of subjects in the FAS.

As described in [Section 9.1.1](#) , the TEAE data will be categorized and presented by SOC, PT, and relationship.

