10.8.2. Ad-RTS-hIL-12 + Veledimex

- Subjects will be given 20 mg of veledimex by mouth, when NPO (excluding other medications) 3 (\pm 2) hours before craniotomy (Day 0). The actual time of veledimex administration should be noted and recorded.
- Surgical planning will be performed on a diagnostic MRI acquired prior to the surgery as per standard of care.
- At the time of tumor resection, tumor, CSF (if available), and blood samples will be collected.
- Immediately after tumor resection, when available, an intraoperative MRI can be performed to identify contrast enhancing or T2/FLAIR hyper intense residual tumor. If intraoperative MRI is not available, the neurosurgeon will select sites for injection.
- [REDACTED]
- [REDACTED]
- The day of Ad-RTS-hIL-12 administration is designated as Day 0. If Ad-RTS-hIL-12 injection is not performed, subject will not continue with post-resection veledimex dosing.
- After tumor resection and Ad-RTS-hIL-12 injection, veledimex will be administered orally for 14 days. The first post-resection veledimex dose is to be given on Day 1. Subsequent veledimex doses are to be taken once daily, in the morning and within approximately 30 minutes of a regular meal.

Subjects should be carefully monitored for possible local reactions and/or hypersensitivity reactions, according to standard practice. Intracranial bleeding or other procedure-related events should be evaluated before the first veledimex dose is given post Ad-RTS-hIL-12 administration. Any changes in neurological status should be reported to the investigator immediately, either during hospitalization or once subject is discharged. Subjects should be instructed to call the study physician or study nurse if they develop any symptoms after they are released from the hospital.

NOTE: It is important that subjects are instructed to maintain adequate oral hydration while subjects are being administered veledimex. Study sites should monitor subjects for proper hydration and monitor blood pressure regularly. The incidence of low blood pressure to date has been lower in glioblastoma subjects as compared with breast cancer or melanoma subjects, likely because a lower dose of veledimex is used in glioblastoma.

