For AEs that occur prior to the administration of investigational product, an assessment of protocol relatedness must be made. AEs may occur due to procedures required during the screening process (e.g., blood collection, washout of an existing medication) prior to the initial administration of investigational product. For AEs that occur before administration of investigational product, only those that are assessed by the investigator as protocol-related should be reported to the sponsor. The following guidelines should be used by investigators to assess the relationship of an AE to a protocol-required procedure:

- Protocol-related: The event occurred due to a procedure or intervention that was described in the protocol for which there is no alternative etiology present in the subject's medical record.
- Not protocol-related: The event is related to an etiology other than the study procedure (the alternative etiology must be documented in the study subject's medical record).

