4.5.2. Full Analysis Set (FAS)

The Full Analysis Set (FAS) includes every subject who received at least one dose of any study drug recorded in the Data Management (DM) database excluding screen failures.

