7.2.2. Treatment Compliance and Modifications

For Ad-RTS-hIL-12 and cemiplimab, the number and proportion of subjects receiving treatment will be summarized at each scheduled dosing visit.

For veledimex, compliance will be calculated for each subject by making the determination whether a subject takes all doses of study drug as instructed. The number of capsules taken will be calculated by subtracting the number of capsules returned from the number of capsules dispensed. The overall study drug compliance (%) will be calculated by dividing the total number of capsules taken during subject's study period by the total number of capsules expected to be received based on the schedule of events and then multiplying by 100.

Compliance (%) = [(total no. of capsules dispensed – total no. of capsules returned) / (No. of days in interval *No. of capsules prescribed per day)] * 100.

Summary statistics on percentage of veledimex compliance as well as the number and percentage of subjects in each compliance category (<80%, 80-100% compliant) will be presented overall.

A subject is considered compliant to veledimex if overall study drug compliance is greater than or equal to 80%. A categorical summary of whether subjects were compliant (yes/no) will be presented.

Percentages will be calculated out of the number of subjects who were dosed in the FAS.

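### SAP 9.1.4 reports relatedness by product, but takes the percentages out of the FAS and counts a blank as Related without asking whether the product had been given

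*SAP*

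**What the plan says.** SAP 9.1.4 promises that relationship "to Ad-RTS-hIL-12 + veledimex and cemiplimab will be presented separately in a table by incidence of occurrence". The investigator has five categories, and none means not applicable. For the summary table, "TEAEs that are missing a relationship or with a relationship other than" Not Related or Unlikely become Related; the listing keeps the blank. The section then states: "Percentages will be calculated out of the number of subjects in the FAS".

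Three other definitions bear on this:

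- **FAS (SAP 4.5.2):** it "includes every subject who received at least one dose of any study drug recorded in the Data Management (DM) database".
- **TEAE (SAP 9.1.1):** the first limb is an event that "Begins on or after the first dose of study drug and before the stop of study drug + 90 days". SAP 8.1 identifies the first study drug as cemiplimab at Day -7.
- **Default denominator (SAP 4.6):** subjects in that treatment, unless another is specified. Section 9.1.4 specifies another.

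The protocol foresees subjects who miss a component. Section 10.8.2 says: "If Ad-RTS-hIL-12 injection is not performed, subject will not continue with post-resection veledimex dosing". Section 9.5 keeps every dosed subject in the safety assessment.

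**The concern.** Safety is half of the primary objective, and the regimen has three components. The 9.1.4 summaries are where the SAP would attribute toxicity to the vector and its activator rather than to the checkpoint inhibitor. A product-specific rate should be a rate among people exposed to the product, for events it could have caused. As written, a subject who never received Ad-RTS-hIL-12 or veledimex counts in their denominator. A blank can also put an event in their numerator before either was given, or in a subject who received neither. The first lowers the reported rate and the second raises it, so neither the sign nor the size of the net error can be assumed. SAP 7.2.2 uses a narrower base for veledimex compliance: "Percentages will be calculated out of the number of subjects who were dosed in the FAS".

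**Working it through.** The plan states no figure for this point, so there is nothing to reproduce. The check sets the definitions together and shows what they can produce.

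**Inputs from the documents**

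- FAS size: N = 40 (SAP 4.4).
- First cemiplimab dose: Day -7, plus or minus 3 days (SAP 3.4; Protocol Table 1).
- First veledimex dose: Day 0 (SAP 7.2.1.3). Ad-RTS-hIL-12: Day 0 (SAP 11.5).
- TEAE clock: starts at the first dose of study drug, which is cemiplimab.

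**Lead-in on cemiplimab alone:** 7 - 3 = 4 days, 7 days, or 7 + 3 = 10 days. Events in this window are already TEAEs. If the relationship to Ad-RTS-hIL-12 + veledimex is blank, 9.1.4 tabulates them as Related to that pair.

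**Not in the documents, so assumed**

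- u: FAS subjects who received neither Ad-RTS-hIL-12 nor veledimex.
- b: subjects counted as Related only because of a blank on an event that preceded the pair, or that occurred in a subject never given it.
- x: exposed subjects with a TEAE properly counted as related to the pair.

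**Formulas**

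- SAP percentage = 100(x + b)/40
- Exposure-based percentage = 100x/(40 - u)
- Ratio of exposure-based to SAP percentage when b = 0: 40/(40 - u), which is 1.026 at u = 1, 1.053 at u = 2 and 1.111 at u = 4
- Each subject in b adds 1/40 = 2.5 points

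**Illustration with x = 20**

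| u | b | SAP % | Exposure-based % |
|---|---|---|---|
| 0 | 0 | 50.0 | 50.0 |
| 0 | 2 | 55.0 | 50.0 |
| 2 | 0 | 50.0 | 52.6 |
| 2 | 1 | 52.5 | 52.6 |
| 4 | 0 | 50.0 | 55.6 |
| 4 | 4 | 60.0 | 55.6 |

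The errors can nearly cancel (u = 2, b = 1), but neither corrects the other.

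**Related sections**

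- 9.1.6 uses the same blank rule, but by study drug as a whole. Events counted from the first dose follow cemiplimab, so the product-level problem does not arise.
- 9.1.7 is split by product and uses the FAS, with an unexplained reference to a subgroup category. It selects on drug withdrawal and has no relationship rule, so only the denominator is at issue.
- 9.1.2 moves an incomplete onset date in the month (or, if the month is missing, the year) of first dose to the first study-drug dose date when the event ended on or after that date. A post-injection event can therefore be dated to Day -7, and a plain onset cut-off at Day 0 would misplace it.

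**The case against.** **Blanks are controlled upstream.** Protocol 14.6 requires a causality assessment for each event, Protocol 17.1 tells sites not to leave fields blank, and SAP 4.4.1 allows lock only once queries are resolved. The investigator can enter Not Related for a lead-in event. Counting a residual blank as Related is a conventional conservative choice. This stands: b should be small, and the rule is faulty only where the product had not been given.

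**The FAS denominator follows the protocol.** Protocol 16.6.2 applies the safety population to all safety variables. Exposure is tabulated separately, so a reader could rescale. That supports the FAS for overall TEAE tables. It does not make the FAS the right base for a percentage that names one product.

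**The product split may never appear.** Both table lists in the SAP appendices show only pooled treatment-related tables (14.3.1.3 and 14.3.1.13). This also stands. Section 10 does not withdraw 9.1.4, so text and list disagree.

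Two stronger readings are not supported:

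- *A reader might infer that the protocol makes blanks normal between Day -7 and Day 0.* Protocol 14.5 says "For AEs that occur prior to the administration of investigational product, an assessment of protocol relatedness must be made". That text concerns screening events before any investigational product. Cemiplimab is one of those products, so ordinary causality assessment applies once it has been given.
- *A reader might infer uninjected subjects from the plan to accrue 36 for about 25 evaluable.* Per-protocol status also requires cemiplimab at Day -7, post-injection veledimex and cemiplimab, and no major deviation. An injected subject can fail on several of these. SAP 4.1 says nobody was replaced, but replacement was optional, so that does not settle u either.

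**Conclusion.** The point holds as a defect in the stated rules. Section 9.1.4 can dilute the rate for Ad-RTS-hIL-12 + veledimex by including unexposed subjects, and can count a blank as Related to products not yet given. At N = 40, the exposure-based rate is 40/(40-u) times the FAS-based one, and each subject counted only through such a blank adds 2.5 points. Both u and the number of blanks are unknown; if both are zero, nothing changes. The cemiplimab summary is largely unaffected because cemiplimab is given first. The change is worth making because it is cheap and these would be the summaries that separate vector toxicity from checkpoint-inhibitor toxicity. The documents do not show that any event has been misattributed.

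**What to change.** In SAP 9.1.4:

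- **(a) Denominator.** Use subjects who received at least one dose of the product concerned. For the pair, that means any dose of Ad-RTS-hIL-12 or veledimex, with the injected N also shown, so that someone given only pre-operative veledimex is not lost. Keep the FAS for overall TEAE tables. Apply the same principle to the product-specific discontinuation tables in 9.1.7.
- **(b) Blanks.** Impute Related to a product only if the subject received it and the event's onset or worsening is on or after its first dose, or cannot be shown to precede it. For partial dates, keep the conservative Related rather than relying on the date imputed under 9.1.2.
- **(c) Entered values.** Never override a relationship the investigator recorded. Query and list Related entries that precede exposure.

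Forcing every event with onset before Day 0 to Not Related would be worse than the present rule. It would erase attribution for events that begin in the lead-in and worsen after injection, and for events whose partial dates are imputed to Day -7.

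Section 9.1.6 needs no product-level change. Reconcile the table list with the split promised in 9.1.4, either by adding the tables or by withdrawing the promise.

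The cost is SAP wording and flags derived from dosing dates that the exposure dataset (ADEX in Appendix 2) should already hold. Appendix 2 marks the adverse-event tables as done, so some output would be added or rerun. Product-specific tables will carry their own N, which needs a footnote.
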